1 STUDY SUMMARY

1.1 Synopsis

Title:	Open label comparison of injectable extended release buprenorphine (CAM2038, Brixadi®) and naltrexone (Vivitrol®) for the treatment of opioid use disorder
Short Title:	Brixadi and Vivitrol
Study Description:	
This study will elucidate the cognitive mechanisms of response to opioid agonists and antagonists used to prevent relapse in OUD through investigation of the underlying neural circuits. We shall use previously validated cognitive probes, functional Magnetic Resonance Imaging (fMRI), and extended-release injectable preparations of opioid partial agonist buprenorphine (XR-BUP, Brixadi) and opioid antagonist naltrexone (XR-NTX, Vivitrol), in OUD patients. Using two medications with opposing mu opioid receptor action will allow a comprehensive evaluation of the mechanisms of response to relapse prevention pharmacotherapy in OUD. The study will determine the presence of treatment effects in the domains of executive function, incentive salience, and resting functional connectivity and the interaction that will indicate a difference between the two medications. Then we will evaluate the ability of the brain fMRI signal to explain relapse defined by % of opioid-positive urine tests and adherence to the study interventions. Participants will be recently detoxified treatment-seeking patients with OUD who will receive 3 monthly injections of XR-NTX or XR-BUP and have weekly urine toxicology monitoring. The project will enroll 200 participants over 6 years. The proposal would be the first neural systems' level investigation of the cognitive effects of the next generation extended release preparation of buprenorphine and naltrexone to explain the individual heterogeneity of OUD treatment response and failure. This project has the potential to advance the theory and personalized treatment of OUD by elucidating the brain mechanisms of vulnerability to relapse in OUD and in SUD in general.
 
The proposal is similar to an existing UPenn IRB protocol 814234 and Biomarkers of disease and response to treatment in opioid addiction in all aspects except the addition of XR-BUP, Brixadi.

Objectives:	Compare brain fMRI response to injectable extended-release buprenorphine (Brixadi, XR-BUP) and naltrexone (XR-NTX, Vivitrol)

**Medications
and
Interventions**

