The clinical management of XRBUP is similar to XRNTX except that induction to XRBUP requires partial detoxification followed a weekly dose of injectable XRBUP, while induction on XRNTX requires complete abstinence (Lofwall et al 2018). The goal of the detoxification and induction phase of the experiment is to establish a uniform starting point for both monthly formulations. To achieve it, we will detoxify all participants to abstinence and randomize after abstinence from illicit opioids has been achieved. Outpatient detoxification to abstinence takes between 5 and 10 days. Following detoxification, the XRBUP participants will receive a combination of 8mg, 16mg, and 24mg strengths of weekly XRBUP, not to exceed 32 mg/week, followed by the injection of 64mg, 96mg, or 128mg of monthly XRBUP. If clinically indicated, supplemental doses of sublingual buropenorphine/naloxone (Suboxone) may be used. If clinically indicated, the induction procedure may be extended by up to one week, using the same approach. The total duration of induction to Brixadi will not exceed 14 days. The XRNTX participants will receive 50 mg of oral naltrexone for 7-10 days after detoxification followed by the 1st XRNTX (380 mg naltrexone IM) injection. The use of symptom-driven titration of weekly XRBUP during induction reflects current best practices in administration of the drug and increases participant safety and comfort. The XRBUP induction period is also intended to synchronize the timepoint at which both cohorts begin their monthly treatments. The non-opioid detoxification will follow the procedure described in our previous neuroimaging studies (Langleben et al 2014, Langleben 2015, Wang et al 2018). Participants who are opioid-positive upon screening will undergo office-based withdrawal management (detox) by the study physicians using FDA-approved generic medications to alleviate opioid withdrawal symptoms following a symptom-triggered approach that includes clonidine 0.1 mg tid, dicyclomine 20 mg qid, clonazepam 0.5 mg q12 hrs PRN, diphenhydramine 25 mg PRN, non-steroidal anti-inflammatory medicines PRN, Trazodone 50 mg qhs and oral hydration solutions (Molenberghs et al 2005). The induction to XRNTX or XRBUP will commence immediately after the baseline MRI session. The 1st monthly injection will be administered by an experienced nurse practitioner after induction is completed (approximately 7-14 days later).

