Neuroimaging (MRI): The MRI session will take place after detoxification and immediately before MAT induction (Table 1, Figure 1). This baseline time-point has been used successfully in our prior studies (Langleben et al 2014, Wang et al 2015) Participants will be escorted to the MRI facility where the investigator will meet them, review the consent and MRI screening form, and answer any remaining questions. Participants will be placed in the scanner in a supine position. The stimuli are rear projected to the center of the visual field using a PowerLite 7300 Video projector system (Epson America, Inc.) and viewed through a mirror mounted on the head coil. Participants will be given a non-ferromagnetic scroll wheel (FORP™, Current Design Inc., Philadelphia, PA) to respond during the tasks. Neuroradiologists will review the scans for clinically significant abnormalities. fMRI data will be acquired during (a) MPRAGE T1 image acquisition (5 min), (b) resting-state fMRI (5 min), (c) Go-NoGo task (5.5 min), (d) visual opioid cue task (10.5 min). The Go-NoGo and the visual opioid cue task will be counterbalance between scan 1 and 2. The total time in the scanner, including time for positioning removal and structural imaging, will not exceed 60 minutes.

STUDY MEASURES: will be administered by the study coordinator or psychologist with appropriate level of clinical training and certification (MA, PsyD or PhD):

Demographic and Clinical (Appendix Section 12.1): We use PhenX protocols (phenxtoolkit.org).

Demographical Information: Standard demographical information will be collected during phone screening and baseline study appointments, such as height, weight, preliminary fMRI eligibility, contact information, years of education etc.

MINI International Neuropsychiatric Interview (MINI) (Sheehan DV, 1998; 59(suppl 20)). The MINI is a clinician administered neuropsychiatric interview for symptoms across 17 of the most common mental health disorders. The DSM-5 version of the MINI will be administered.

Addiction Severity Scale Lite (ASI-Lite) (McLellan, 1997) The Addiction Severity Scale Lite is a shortened version of the full clinical interview. The measure collects information on demographics, employment, legal status, alcohol/drugs, family/social relationships, and psychiatric status. This measure is administered by a clinician.

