9 STATISTICAL CONSIDERATIONS

9.1 Statistical Hypotheses

Overview of primary hypotheses: Our primary response will be a binary indicator of treatment failure on the XRNTX or XRBUP regimen, defined as ≥ 2 weekly UDS positive for opioids, or self-report of ≥ 2 periods of three or more days of opioid use, or refusing XRNTX or XRBUP, or dropping out of study entirely. In hypotheses H1a and H1b, we are examining the effects of small, pre-specified, sets of measures, so our analyses will focus on model fit and prediction, and not on model selection. In hypothesis H1c, we search for best sets of predictors among demographic and clinical-behavioral variables, and over sets of brain/neural measures, so our focus is on model selection and on avoiding overfitting to the available data.

R61 Phase:

Hypothesis H1 (fMRI): For each of the cue reactivity (H1a), response inhibition (H1b), and connectivity (H1c) brain measured, we have a small number of neural responses associated with one or two regions of interest. These variables are continuously distributed, so we will test Hypotheses 1a, 1b and 1c using a repeated measures analysis of variance (rm-anova). The models will include a within-subject factor for Session (PRE vs ON) and a between-subject factor Group (XRNTX vs XRBUP), and their interaction. To accommodate the anticipated non-normal distributions of the response, we will use a generalized estimating equation (GEE) approach, using robust standard errors, using a compound symmetry working correlation structure for the within-subject correlations between the PRE and ON fMRI scans (Diggle PJ et al 2002). We will perform the rm-anova separately for each ROI (mPFC and VS for H1a, IFC for H1b, and VS-rtIFG and VS-mPFC for H1c). The hypotheses will be addressed by the Session by Group interaction, and we will obtain estimates and standard errors of the PRE vs ON change within each of the two groups, along with the size, standard error and significance of the differences between these estimates.

Sample size considerations for sample: The sample size is adequate for application of the GEE methods to obtain robust standard error (Lipsitz et al 1994). For a test of the PRE vs ON effect, our sample yields 80% power for a one-sided test that the ON levels will be Cohen's $d=0.4$ lower than the PRE levels, consistent with a decrease of Cohen's $d=0.5$ observed in our preliminary data and a decrease of Cohen's $d=0.3$ in the Suboxone sample.

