Analyses of effects of neural response on relapse vulnerability: We consider the effect for an individual neural change variable, in a model where Group is included, assuming a small effect for Group (odds ratio = 1.25). We have three domains, with two neural variables in two domains and one in the other, so we provide power for $\alpha=0.05$ and for $\alpha=0.025$. For $\alpha=0.05$ we have 80% power for an odds ratio of 1.75 or higher per standard deviation increase in a neural variable; for $\alpha=0.025$, we have 80% for an odds ratio of 1.86 or higher.

Analyses of polysubstance use outcomes: We will also examine the effects of Group and neural change variables on other substance use outcomes, including self-report and UDS measures of opioid, stimulant, and benzodiazepine use. Here, we will use the self-report and UDS measures to create binary weekly measures of use for each substance, and use GEE repeated measures logistic regression models, with Group and the neural change measures as predictors, to estimate and test effects. These secondary analyses will be subject to missing data. We anticipate 25% dropout rates. To assess possible effects of nonignorable missingness on inference, we will perform sensitivity analyses using pattern-mixture models and selection models. For pattern mixture models, subjects are grouped on the basis of their pattern of missing data, and the resulting categorical factor is included in the analyses as a main effect and interaction with predictors of interest. Overall predictor effects may be found by averaging over the patterns (Molenberghs et al 2005). Selection models (Molenberghs et al 2005) take a different approach, by explicitly modeling the probability of drop out, and incorporating the predicted probabilities into the main longitudinal analysis, with the dropout and response processes included in a single bivariate model. Comparisons between the predictions of the primary analyses, and each set of pattern mixture and selection models, provides some evidence for assessing the sensitivity of results to missing data.

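### The Phase 1 power figure is for PRE-to-ON change, which this design cannot attribute to either drug; drug conclusions should rest on the Group-by-Session interaction, and Phase 1 should state its precision.

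*Combined protocol and SAP*

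**What the plan says.** The Synopsis (1.1) makes two promises in one sentence. The first is "The study will determine the presence of treatment effects in the domains of executive function, incentive salience, and resting functional connectivity". The second is an interaction that would show a difference between the two medications. H1, in section 3.2 and again in 9.4.1, has the same two parts: each drug modulates brain activity from PRE to ON, and the response differs between drugs.

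In section 9.1 (R61 phase), the rule for deciding H1 is clear: "The hypotheses will be addressed by the Session by Group interaction". The sample-size paragraph that follows addresses a different effect: "For a test of the PRE vs ON effect, our sample yields 80% power for a one-sided test that the ON levels" will fall below PRE by d=0.4. It supports this as "consistent with a decrease of Cohen's $d=0.5$ observed in our preliminary data and a decrease of Cohen's $d=0.3$ in the Suboxone sample". It states neither the number analysed nor alpha, and no interaction power or precision is given for Phase 1.

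On design, section 3.1 describes two groups, both on active medication. On the baseline scan, section 6.1 says "The MRI session will take place after detoxification and immediately before MAT induction". Participants who are opioid-positive at screening are first managed with a "symptom-triggered approach that includes clonidine 0.1 mg tid, dicyclomine 20 mg qid, clonazepam 0.5 mg q12 hrs PRN", among other medicines. The Schedule of Activities (13.1) puts the second scan at day 55. The limitations section (10.2) does not discuss what else changes between the two scans.

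**The concern.** A PRE-to-ON contrast without a concurrent untreated or time control measures everything that differs between the two sessions. Here that includes recovery from withdrawal, clearance of the detoxification drugs (section 2.3.1 names over-sedation and hypotension as common side effects), a second exposure to the scanner and tasks, and regression to the mean. All can act in both arms. H1a and H1b predict a fall in signal, a direction that these processes could also produce.

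The risk is one of interpretation. A significant fall in one arm, or in both arms pooled, could be reported as XRNTX or XRBUP changing the brain response, with the Synopsis, H1 and a planned one-sided test cited in support. A second problem is that the stated 80% justifies the Phase 1 sample by an effect other than the one that answers H1 and drives the decision to go on to Phase 2.

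**Working it through.** **Inputs from the documents.** Phase 1 recruits 60 (3.1). About 75% are expected to reach the first monthly injection, and 10% extra scanner time is budgeted for data loss (5.3). The PRE vs ON effect is d=0.4, one-sided, 80% power, set against 0.5 and 0.3 (9.1). The anticipated interaction is d=0.42 in mOFC and 0.38 in VS (9.1, 9.2). The milestone is an interaction of d≥0.2 (3.2, 9.1, 9.4.1).

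**Assumptions.** Alpha is 0.05 one-sided (9.1 gives alpha only for the relapse models). Allocation is 1:1. The 10% scanner allowance is read as 10% of scans lost. Each d is in SD units of the PRE-ON change score.

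**1. Reproducing the 80%.** For a paired test, n = ((1.645 + 0.842)/0.4)² = 38.6, so 39 by the normal formula. The noncentral t gives 80.0% at n=40. The documents' own attrition figures lead to the same number: 60 × 0.75 × 0.9 = 40.5. With 45 participants power is 84%, and with all 60 it is 92%. At one-sided 0.025 the normal formula needs 49.1, so 50. On this scale either alpha needs more than one arm's 30 participants, so the figure is for both arms pooled.

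**2. The same test within one arm** (noncentral t, one-sided 0.05):

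| d | n=20 | n=30 |
|---|---|---|
| 0.5 | 69.5% | 84.8% |
| 0.4 | 53.2% | 69.0% |
| 0.3 | 36.3% | 48.4% |

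The 80% at d=0.4 therefore does not apply to each medication separately.

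**3. Checking the scale.** For the full-sample interaction with 70 per group and d=0.42: 0.42/√(2/70) − 1.645 = 0.84, which is 80.0% power. Section 9.1 states 81%, so the change-score scale agrees with the plan's own. If d were instead in single-session SDs, the step 2 figures would depend on the PRE-ON correlation, which is not stated. A correlation of 0.5 gives the same results; at 0.7 an arm of 30 would have 87% at d=0.4.

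**4. Precision of the Phase 1 interaction estimate.** The 95% half-width is 1.96 × √(2/n per arm):
- 30 per arm: 1.96 × 0.258 = 0.51 SD
- 20 per arm: 1.96 × 0.316 = 0.62 SD

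That is 2.5 to 3.1 times the 0.2 threshold. If the drugs did not differ, a single region's estimate would reach +0.2 with probability 1 − Φ(0.2/0.258) = 22% at 30 per arm and 1 − Φ(0.2/0.316) = 26% at 20. This is for one region, not for the whole milestone.

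**5. Context.** Phase 1 power for the interaction, one-sided 0.05, 20 to 30 per arm, is 37-49% at d=0.42 and 32-42% at d=0.38.

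**The case against.** The strongest reply is that the plan already decides by the interaction. The Synopsis names it as the primary endpoint, H1a to H1c each compare XRNTX with XRBUP, and the milestone uses it. The model paragraph in 9.1 asks only for estimates and standard errors of within-group change, and attaches significance to the difference between groups. No decision rule rests on within-arm change. All of this stands and limits the point to wording and to the Phase 1 justification. It does not remove the point, because the Synopsis and H1 make a separate claim for each drug and the sample-size paragraph describes a one-sided test of PRE vs ON.

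A reader might infer from the 37-49% that Phase 1 is underpowered and the design fails. The documents do not support that. Phase 1 is a feasibility phase whose aim is to estimate, and its go rule is an estimated effect size. Section 4.1 says that the confirmatory questions need a sample that neither phase reaches alone, and 9.1 places the formal interaction test in Phase 2 with its own power statement.

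Pooling the arms is not an error either: 0.4 is the midpoint of 0.5 and 0.3, which is coherent for a group-averaged Session effect.

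The alternative explanations should not be overstated. Detoxification drugs go to those opioid-positive at screening, by symptom and partly as needed, not to everyone. The documents do not say whether the same images are shown at both scans, so habituation to identical stimuli cannot be asserted.

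**Conclusion.** The point holds as one of attribution and of a mismatched sample-size statement. Within-arm or pooled PRE-to-ON change cannot be assigned to XRNTX or XRBUP in this design. The interaction can support a randomised conclusion, but only about the difference between the drugs, and only among participants who reach the second scan.

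The stated 80% is arithmetically sound for about 40 pooled participants, but it answers a question other than H1. The figure relevant to the Phase 1 decision is the interaction half-width, about ±0.51 to ±0.62 SD for 30 down to 20 per arm. These sizes rest on the assumed alpha, allocation, analysable numbers and change-score scale.

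The primary endpoint, the milestone's reliance on the interaction and the place of the formal test in Phase 2 are unaffected. A reader might also infer that adjusting for COWS and SOWS would make within-arm change interpretable. It would not: scores at the ON scan are post-treatment, and section 2.2.1 lists relief of withdrawal-like symptoms among buprenorphine's actions, so adjustment could remove part of a drug effect and would leave time and repeat scanning untouched.

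**What to change.** 1. In 1.1, 3.2 (H1), 9.1 and 9.4.1, add a statement such as: Change from PRE to ON within an arm, or averaged over arms, is descriptive; conclusions about the drugs rest on the Group-by-Session interaction, which estimates the difference between XRNTX and XRBUP and not the effect of either alone.
2. In 9.1 (R61 phase), replace the PRE vs ON power sentence with the precision of the interaction estimate that drives the d≥0.2 milestone: a 95% half-width of about ±0.51 SD with 30 analysable participants per arm and ±0.62 SD with 20. State the analysable number assumed, how it follows from the 60 recruited, and the alpha.
3. Do not add a COWS- or SOWS-adjusted analysis of within-arm change for this purpose.

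The cost is protocol and SAP wording only, with no change to arms, visits, scans or sample size. The drawback for the sponsor is that the Phase 1 figure will look less favourable than 80% power.
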